9.21 Stopping Rules

The DSMB will monitor the safety of the subjects during the course of the study. The DSMC can recommend changes to the protocol or temporary stopping of the trial at any time if there are significant safety concerns. The DSMC Charter will include recommended safety stopping rules.

9.22 Follow-Up and Final Reports

The investigator shall provide Enterin, Inc. with an accurate final report within 1 month after completion, termination or discontinuation of the study. The final report may not precede retrieval of case report forms which have not been monitored.

9.23 Regulatory Aspects

Neither the investigator nor Enterin Inc. shall modify this protocol without first obtaining concurrence of the other in writing. All changes must be submitted to the IRB. Protocol

modifications which impact patient safety or the validity of the study must be approved by the IRB and submitted to the FDA before implementation. In the case of a medical emergency to increase safety of patients, a change may be made after discussion with the sponsor. In these instances the IRB and FDA will be notified as soon as possible.

10 DATA MANAGEMENT AND STATISTICS

This is a trial with two stages. The Stage 1 portion will consist of 10 patients who will be dose escalated in single doses. Each patient will proceed through all the dose escalations starting at 25 mg and ending at 200 mg or at the dose at which s/he experiences a dose limiting toxicity (DLT). The doses to be tested are 25mg, 50mg, 75mg, 100mg, 125mg, 150mg, 175mg and 200mg. In the Stage 2 portion, all patients will go through a multiple dose escalation (3 dosing days at each dose) and the dose at which the patient experiences a consistent pro-kinetic effect (spontaneous, complete stool in at least 2/3 consecutive doses) without a DLT will be the dose for that patient. Patients who experience a DLT prior to reaching their pro-kinetic dose and at a dose equal to or less than the STDE dose will be terminated. Otherwise the patient will be assigned the highest dose at which they did not experience a DLT. If the patient reached 175 mg without a DLT and without a pro-kinetic dose, her/his dose will be 175 mg. The primary endpoint for the Stage 1 study is to determine whether the dose levels explored are safe and tolerable. The primary endpoint for the Stage 2 study is the regularization of bowel function as determined by stool frequency at the end of the fixed dose period compared to baseline. The Stage 2 portion will enroll 40 patients, with a target sample size of 34 evaluable patients. Six extra patients are enrolled to allow for patient withdrawals or terminations prior to the completion of the trial.

10.1 Sample Size/Power Considerations

10.1.1 Stage 1

There will be 10 patients enrolled in Stage 1. Two patients will be started on the 25mg dose. If no DLTs are observed, they will be escalated to the next dose and the remaining 8 patients will be started at 25mg. Each dose level will be a single dose and patients will be observed for three days before being given the next higher single dose. It is intended that each patient receive a single dose of each of the levels: 25mg, 50mg, 75mg, 100mg, 125mg, 150mg, 175mg and 200mg. However, if a patient experiences a DLT, they will not be further escalated.

A DLT is defined in Section **9.8** using the Common Terminology Criteria for Adverse Events (CTCAE), as a grade 2 vomiting within 24 hours of taking ENT-01 grade 2 diarrhea within 24 hours of taking ENT-01, grade 2 abdominal pain within 24 hours of taking ENT-01, grade 2 postural hypotension within 24 hours of taking ENT-01. Additionally, an LFT elevation > 3xULN within 24 hours of taking ENT or any gastrointestinal AE > grade 3 within 24 hours of taking ENT-01 that is at least possibly attributable to ENT-01 will be considered dose-limiting toxicity for the purpose of analyses.

There is no power calculation for the Stage 1 portion because it is merely trying to determine whether ENT-01 is safe and tolerable for these levels. The PK analyses will be descriptive and are meant to understand how ENT-01 is metabolized.

10.1.2 Stage 2

The target sample size for Stage 2 is 34 evaluable patients and an additional 6 patients will be accrued to allow for patient drop-outs and terminations; these 40 patients will be different from the 10 patients accrued to Stage 1. A patient is evaluable if s/he has baseline measurements (obtained at the end of the run-in Period, 3.1) and measurements at the end of the fixed dose period (end of Period 3.2). The primary endpoint for Stage 2 is average complete spontaneous stool frequency increase by 1 point over baseline, OR 3 or more complete spontaneous stools per week. A patient will be labeled as a "success" if s/he meets one or more of the criteria above, otherwise the patient will be labeled as a "failure". The primary analysis compares the proportion of patients deemed a success at the end of the fixed-dose period (end of period 3.2) to 0.10, which is the highest proportion of spontaneous resolution of constipation assuming no treatment. A patient is deemed a success or failure by comparing the assessment at the end of the fixed-dose period (Period 3.2) to baseline (obtained at the end of the run-in period, Period 3.1). There could be between 34 and 40 patients with these measurements and each patient will be labeled as a "success" or "failure". It is assumed that without treatment, the success rate would be 10% (null hypothesis). An exact binomial test with a 0.05 two-sided significance level will have 80% power to detect the difference between 0.10 (proportion expected if patients are not treated), p₀, and an ENT-01 proportion, p_E , of 0.29 (0.27) when the sample size is 34 (40). It is assumed that most patients will be deemed a success on the ENT-01 arm and so the study is adequately powered.

10.2 Data Collection and Case Report Form Monitoring

Reports will be generated on a weekly basis to monitor data completeness. Sites and patients who are missing data will be contacted and measures will be taken to resolve any obstacles regarding the data submission.

10.3 Endpoint definitions and measurements

10.3.1 Assessment of Safety

Safety assessments (vital signs, physical examinations, interim medical history, vital signs, EKG (when clinically warranted for any unscheduled EKG), AEs, clinical laboratory results (routine hematology and biochemistry) are to be performed at protocol-specified visits, as specified in the Schedule of Procedures and Assessments.

Vital Signs

Vital signs (body temperature, respiration rate, heart rate, systolic and diastolic blood pressure measurements) will be evaluated at the visits indicated in the Schedule of Procedures and Assessments. Blood pressure will be taken twice. The first time, the patient shall be lying down. The second blood pressure will be taken within 5 minutes of sitting or standing from the recumbent position. All other vital signs will be measured after the patient has been resting in a sitting position for at least 5 minutes. Blood pressure measurements are to be taken in the same arm for the duration of the study. Body weight (without shoes) will be recorded whenever vital signs are recorded, and height (without shoes) will be recorded at screening only.

Vital sign measurements will be repeated if clinically significant or machine/equipment errors occur. Any confirmed, clinically significant vital sign measurements must be recorded as AEs.

Physical Examination

A complete physical examination (head, eyes, ears, nose and throat, heart, lungs, abdomen, skin, cervical and axillary lymph nodes, neurological, and musculoskeletal systems) will be performed at Visit 1. Physical examinations will be performed by a physician. In addition, medical history will be recorded at screening, including smoking history, if applicable.

A limited (brief) physical examination to verify continued patient eligibility and to follow up any change in medical history will be performed at the visits indicated in the Schedule of Procedures and Assessments. Symptom-driven limited physical examinations will be performed as clinically indicated at any study visit. All changes not present at baseline or described in the past medical history and identified as clinically noteworthy must be recorded as AEs.

Electrocardiogram (EKG)

A 12-lead resting EKG will be obtained at the visits indicated in the Schedule of Procedures and Assessments.

An assessment of normal or abnormal will be recorded and if the EKG is considered abnormal, the abnormality will be documented on the CRF. EKGs will be repeated if clinically significant abnormalities are observed or artifacts are present.

Laboratory Assessments

Laboratory assessment samples are to be obtained at designated visits as detailed in the Schedule of Procedures and Assessments.

All clinically significant laboratory values should be captured on the CRF as AEs.

Blood and urine samples will be analyzed at the laboratory facility at the Investigational site. Urine samples will be analyzed by dipstick, and a microscopic analysis will be performed if the results of dipstick indicate abnormalities to be further investigated. All laboratory reports must be reviewed, signed, and dated by the Investigator. A legible copy of all reports must be filed with both the patient's CRF and medical record (source document) for that visit. Any laboratory test result considered by the Investigator to be clinically significant should be considered an AE (clinically significant AEs include those that require an intervention). Clinically significant abnormal values occurring during the study will be followed until repeat test results return to normal, stabilize, or are no longer clinically significant.

Adverse events

All reported AEs will be coded using the CTCAE version 4.03 terminology. The incidence of treatment-emergent AEs (TEAEs; events with onset dates on or after the start of the study drug) and treatment-related AEs will be summarized by system organ class (SOC) and preferred term

(PT). Events with missing onset dates will be included as treatment-emergent. If a patient experiences more than 1 occurrence of the same AE, the occurrence with the greatest severity and the closest association with the study drug will be used in the summary tables. SAEs and AEs that result in treatment discontinuation will be summarized. In addition, AEs of special interest will be summarized by SOC and PT; categories of AEs of special interest include: nausea, vomiting, abdominal pain, diarrhea, and rectal bleeding.

All AEs will be listed by patient, along with information regarding onset, duration, relationship and severity to study drug, action taken with study drug, treatment of event, and outcome.

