CP1001 v0.9, Version Date: 27JUL2017

[figure not shown]
31

kept on that fixed dose for a further 2-4 dosing days (3 days if it falls on a Saturday, 4 days if it falls on a Sunday).

The sentinel group will be a group of 10 patients who did not participate in Stage 1. Patients will be given three consecutive doses of the dose which was found to be safe and tolerable in everybody (STDE) and effective in at least some patients in Stage 1 (75 mg in schematic) at home. Patients will self-administer the study medication *daily* for 3 doses (3 days at each dosing level). The dose will be taken upon awakening on an empty stomach along with 8 oz. of water simultaneously to dopamine). The patient will not be allowed to ingest any food for at least 60 minutes after study medication. The daily diary will be completed and results verbally transmitted and emailed to the study coordinator every evening including on week-end days and entered into the electronic data capture system the same night or first thing in the morning. The coordinator will check in with the patients daily, at the end of the day and determine whether there have been any adverse events or CSBM. If the patient has not produced a CSBM within 24 hours of a dose, on at least two of the three days at a given dose, then the patient will be told to proceed to the higher dose of STDE+25mg (eg. 100mg qd) and also to use a suppository followed by an enema if necessary on the evening of the third day (See rescue diagram below). At the end of the second dosing period (100mg for 3 days), the same criteria will be applied to make a determination as to whether to proceed to STDE+50mg (e.g. 125 mg qd) or not. The incremental dosing will continue up to the consistently clinically effective (pro-kinetic) dose, or to the DLT, whichever comes first. Patients who do not have pro-kinetic effect at DLT will be treated with the highest dose at which they did not have a DLT, if it is at least the STDE dose; if the DLT occurred at the STDE dose, then the patient will be terminated. Should a pro-kinetic response not occur at 175 mg, patients will take 175 mg for the 2-4 additional fixed-dose dosing days and 6 randomized dosing days (assuming randomization is to treatment). DLT will be the dose inducing repeated vomiting or diarrhea within 24 hours of dosing. The lowest dose producing a CSBM on 2/3 consecutive doses will be noted as the pro-kinetic dose (LSTDEi i.e. consistently clinically effective safe and tolerable dose for that particular individual). Patients will be kept on the lowest dose producing a pro-kinetic effect for another 2-4 days prior to randomization in Period 4. The Enterin CMO will review the stool diaries prior to randomization to ensure dosing adequacy. PAC-QOL and PAC-SYM will be repeated prior to randomization at Visit 3. CSBM during the fixed dose period will

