9.12 AE Assessment and Recording

All adverse events, exacerbations of concomitant illnesses, or events known to be related to underlying disease processes or concomitant medications are to be recorded on the case report form throughout the study. If a pre-existing condition worsens on study, the date on which the

exacerbation began should be recorded. Onset dates for study treatment-related adverse events

must be on or after the date of initial study treatment use. The need to record an adverse event on

the case report form is not dependent on whether the adverse event is associated with the use of

the study medication. In order to avoid vague, ambiguous or colloquial expressions, the adverse

event should be recorded in standard medical terminology.

Adverse event recording will include the date of onset, severity, duration, whether or not

the study medication was discontinued or its dosage changed because of the event, the treatment

given and the outcome. The investigator must also assess whether the event was related to the

study medication, concurrent drug therapy, underlying disease, a combination of these factors, or

if it is unknown. Patients with an adverse event should be carefully followed to determine

outcome.

The investigator will use the NCI definitions to grade the severity of the event.

Grade 1: Mild; asymptomatic or mild symptoms; clinical or diagnostic observations

only; intervention not indicated

Grade 2: Moderate; minimal, local, or non-invasive intervention indicated; limiting age-

appropriate ADL

Grade 3: Severe or medically significant but not immediately life-threatening;

hospitalization or prolongation of hospitalization indicated; disabling; limiting

self-care ADL

Grade 4: Life-threatening consequences; urgent intervention indicated

Grade 5: Death

The relationship or association of the study medication in causing or contributing to the

adverse event will be characterized as remote, possible or probable as defined below:

Not related: Evidence indicates no plausible direct relationship to the study medication

CP1001 v0.9, Version Date: 27JUL2017

50

Remote: Suggests other conditions are reasonably likely to account for the event including concurrent illness, progression or expression of the disease state, or reaction to concurrent medication

Possible: Suggests that the association of the event with the study medication is unknown; however, the adverse event is not reasonably supported by other conditions

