7.2.2 Subject Disposition

7.2.3 Subject Disposition for Stage 1

Subject disposition will be summarized for each dose of ENT-01 and overall. Number and percentage of subjects who complete each dose, number and percentage of subjects who discontinued from the study early by primary reasons will be presented. The denominators for calculating the percentages will be based on number of subjects enrolled.

Discontinued subjects will be provided in a data listing.

7.2.4 Subject Disposition for Stage 2

Subject disposition will be summarized for each period and for each analysis population. Number and percentage of subjects who complete the full protocol, number and percentage of subjects who discontinued from the study early by primary reasons will be presented. The denominators for calculating the percentages will be based on number of subjects in the analysis population.

Discontinued subjects will be provided in a data listing.

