7.8 Analysis of Safety Data

7.8.1 Adverse Events

Adverse events will be coded into SOC and PT using the current version of MedDRA. Severity of AEs will be assessed by investigators according to CTCAE (v4.03). In database, Grade 1 is labeled as Mild, Grade 2 as Moderate, and Grade 3 as Severe.

AEs that have a possible, probable or definite relationship to study drug will be defined to be related to the study drug while others will be defined as “not related”. AEs with the closest relationship to the study drug will be used for summary.

The number and percentage of subjects who experienced an AE during escalation and fixed dosing periods will be summarized by dose level (Stage 1: 75 mg up 200 mg; Stage 2: 75 mg up to 250 mg, fixed dose, and washout) and overall for each stage and for the Safety population. The denominator for calculating the percentages will be based on the number of subjects ever exposed to each dose and overall in the Safety Population.

Additionally, the number and percentage of subjects who experienced an AE during randomization period will be summarized by treatment (Placebo and ENT-01). The denominators for calculating the percentages will be based on the number of subjects ever exposed to each treatment in the Randomized Population.

A treatment emergent adverse event (TEAE) is defined as adverse events with a date of onset (or worsening) on or after the start date of a treatment up to the start date of the next treatment. The following types of summaries will be provided:

- Overview of TEAEs
- TEAEs by SOC and PT
- TEAEs by SOC, PT, and Maximum CTCAE toxicity grade
- TEAEs by SOC, PT, and Maximum CTCAE toxicity grade ≥ 3
- TEAEs by SOC, PT, and closest relationship to study drug
- TEAEs by PT in decreasing frequency
- Drug-related TEAEs by SOC and PT
- Drug-related TEAEs by PT in decreasing frequency
- Serious TEAEs by SOC and PT
- TEAEs leading to study discontinuation by SOC and PT
- TEAEs of special interest including nausea, diarrhea, and dizziness by SOC and PT.

If a preferred term or system organ class was reported more than once for a subject, the subject would only be counted once in the incidence for that preferred term or system organ class.

In tabulation by severity (i.e., CTCAE toxicity grade),

- For a given preferred term, only the most severe preferred term for each subject will be included.
- For a given system organ class, only the most severe system organ class for each subject will be included.

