Similarly, in tabulation by relationship,

- For a given preferred term, the most closely related preferred term to the study drug for each subject will be included.
- For a given system organ class, the most closely related system organ class to the study drug for each subject will be included.

Adverse events including baseline AEs, serious adverse events, and adverse events leading to discontinuation from the study will be provided in separate data listings.

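### The protocol promises a summary of AEs that stop treatment; the SAP reports only AEs that end study participation and does not declare the change.

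*Protocol*

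**What the plan says.** Protocol 10.3.1, under adverse events, commits to the following: "SAEs and AEs that result in treatment discontinuation will be summarized". The same section has every AE listed with the action taken on the drug. Protocol 9.12 has the investigator record for each event whether "the study medication was discontinued or its dosage changed because of the event".

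SAP 7.8.1 names one discontinuation table, "TEAEs leading to study discontinuation by SOC and PT", and says that "adverse events leading to discontinuation from the study will be provided in separate data listings". The disposition sections (SAP 7.2.3 and 7.2.4) work on the same basis: the "number and percentage of subjects who discontinued from the study early by primary reasons will be presented".

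SAP section 1 gives the SAP precedence over the protocol's statistical section. SAP 5.1 reports no changes to the protocol's analyses. SAP section 9 declares two dropped success analyses and nothing on adverse events.

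On what follows a DLT, protocol 10.1.1 says for Stage 1 that "if a patient experiences a DLT, they will not be further escalated". For Stage 2, the Period 3.2 text says that patients without a pro-kinetic effect at their DLT "will be treated with the highest dose at which they did not have a DLT", provided that dose is not below the starting (STDE) dose.

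**The concern.** Stopping the drug and leaving the study are different events, and this design has follow-up off drug. If the two can come apart, a table restricted to study exits does not deliver the summary that the protocol promised. Because the SAP takes precedence, the narrower table is the one that would be produced.

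Safety and tolerability are primary objectives in both stages. A reader of the report will look at the discontinuation table to see how often an AE made patients stop ENT-01. A low figure there could mean that few had to stop, or only that those who stopped stayed for washout. The table as specified cannot tell these apart.

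**Working it through.** No power or sample-size figure is involved, so the check is a comparison of the texts followed by one simple calculation.

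1. **Is the change explained by the amendment?** SAP 2.1 says the amendment of 2 February 2018 altered the Stage 2 dose range and removed the randomization period, and nothing else. On that statement the AE commitment in protocol 10.3.1 still stands.

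2. **Can a patient stop the drug for an AE and stay in the study?** SAP 2.1 describes Stage 1 dosing as running to 200 mg or to the dose that produces a DLT, and then places subjects in two weeks of off-drug observation. Protocol 10.1.1 says only that escalation stops. On these passages, yes.

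3. **Follow such a patient through the planned outputs.** Take a Stage 1 patient with a DLT below 200 mg who completes washout.
   - Summary promised in protocol 10.3.1: counted.
   - SAP 7.8.1 study-discontinuation table and listing: absent.
   - SAP 7.2.3 disposition: absent from early study discontinuations, but visible as not completing the later doses, with no AE attached.
   - SAP 7.8.1 general TEAE tables: present by SOC, PT, grade and relationship.
   - SAP 7.8.6 DLT table: present if the event meets SAP 4.3.
   - SAP 7.8.7: the patient's Stage 1 dosing is listed.

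   The event is reported several times, but nowhere as the reason the drug was stopped.

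4. **Does the DLT table stand in for the missing one?** Only in part. Protocol 10.1.1 also treats gastrointestinal AEs above grade 3, at least possibly attributable to ENT-01, as dose-limiting for analysis; SAP 4.3 leaves these out. They would appear in the table of TEAEs of grade 3 or higher, again without a link to stopping. An AE outside the DLT list that leads the investigator to stop the drug has no output of its own.

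5. **Direction.** A patient who leaves the study while being dosed also stops the drug. For events during dosing, study discontinuations are therefore a subset of treatment discontinuations, and the SAP count is at most the protocol's count. An AE in washout that leads to withdrawal is a separate case, since the drug has already ended.

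6. **Size per patient.** With the planned numbers, 1/10 = 10 percentage points in Stage 1 and 1/40 = 2.5 percentage points in Stage 2. The number of such patients cannot be derived, because the protocol is not consistent on who leaves:
   - Stage 1: the individual stopping criteria in Period 2.1 say a patient with a DLT endpoint is terminated, without saying from what. Protocol 10.1.1 and SAP 2.1 say only that dosing ends.
   - Stage 2: the individual stopping criteria in Period 3.2 terminate patients who reach a DLT before a pro-kinetic effect. The Period 3.2 dosing text, its tolerability paragraph and protocol section 10 keep some of them on a lower dose. The dosing text and the tolerability paragraph also disagree on a patient whose highest DLT-free dose is exactly the STDE dose.
   - The Period 4 text ties some Stage 2 tolerability failures explicitly to leaving the study.

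**The case against.** The best defence is that little is lost. Both documents define tolerability through DLT endpoints, and SAP 7.8.6 counts those whether or not the patient leaves. All TEAEs are tabulated, and Stage 1 disposition shows how many complete each dose. If termination after a DLT means leaving the study, the two tables largely coincide. One can also argue that a DLT is a planned end to Stage 1 escalation rather than a discontinuation.

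Much of this stands, and it limits the point. A reader might infer more than the documents support in three ways:

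- **That these events go uncounted.** They do not. Only their attribution to stopping the drug is missing.
- **That dose reductions are part of the discrepancy.** The protocol sentence covers treatment discontinuation only. A Stage 2 patient who steps down after a DLT has not discontinued, and the protocol's own summary would not include that patient.
- **That the Stage 1 dosing schematic gives the scale.** One could try to read 6 of 10 subjects as stopping before 200 mg and set 60% against 0%. The schematic is labelled hypothetical, its cells cannot be read reliably in the available text, and the contrast assumes that all six complete washout. It is not an estimate.

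What does not stand is the claim that other outputs fill the gap. None is specified to show which AEs ended ENT-01. The TEAE overview in SAP 7.8.1 has no stated content, so such a row is possible but not planned. The planned-end argument is a reason to state a convention, not to drop the table.

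**Conclusion.** The mismatch between protocol 10.3.1 and SAP 7.8.1 is real and undeclared. For events during dosing, the SAP's discontinuation table can equal or fall short of the rate at which AEs stopped ENT-01, but cannot exceed it. The shortfall is 10 points per affected patient in Stage 1 and 2.5 in Stage 2. It could be zero if every patient who stops also leaves, and it is probably smaller in Stage 2, where some stops are tied to leaving the study.

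The conclusion rests on two assumptions: that the SAP's account of the February 2018 amendment is complete, since the amended protocol text was not available, and that a Stage 1 patient stopped by a DLT may enter washout, as SAP 2.1 reads. It is a modest but worthwhile correction to reporting on a primary objective.

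**What to change.** In SAP 7.8.1, add a table and a listing of TEAEs leading to discontinuation of ENT-01, by stage and dose at onset, derived from the recorded action taken on the drug (protocol 9.12 and 10.3.1). State whether a Stage 1 escalation ended by a DLT counts. Keep the study-discontinuation table, but derive it from the withdrawal date and reason (protocol 4.5); the action-taken field cannot identify who left the study. If the sponsor prefers not to add the outputs, the change should be declared in SAP section 9.

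A row for TEAEs leading to dose reduction would be an optional addition beyond the protocol's commitment.

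Reconcile the Period 2.1 stopping criteria with protocol 10.1.1 and SAP 2.1, and the Period 3.2 stopping criteria with the Period 3.2 dosing and tolerability text and protocol section 10, so that it is clear who stops the drug and who leaves the study.

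The cost is one table shell, one listing and SAP wording, using data already collected. The reported discontinuation rate may be less favourable.
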